### **1.7.2 Rationale for using a fixed dose**

The results of a population pharmacokinetic analysis in 137 subjects who received MLN9708 in overseas studies suggest that neither body surface area nor body weight appreciably affect MLN9708 clearance or distribution volume. It was concluded that body surface area does not affect the  $C_{max}$  or AUC, so changing to a fixed dose would be appropriate. In addition, since it has been decided that fixed doses will be used in future overseas clinical studies, we concluded that it would be appropriate to use a fixed dose in this Japanese phase 1 study as well. When converting the dose from a body surface area dose to a fixed dose, we used  $1.86 \text{ m}^2$ , which was the mean body surface area of the subjects who participated in overseas clinical studies of bortezomib in multiple myeloma that were conducted by MPI. Converting  $2.97 \text{ mg/m}^2$ , which was the MTD both in MLN9708 monotherapy and in the combined use of MLN9708 with Rd, was converted into a fixed dose, yielded a fixed dose of 5.5 mg, and converting  $2.23 \text{ mg/m}^2$ , which is the recommended dose of MLN9708 when used in combination with Rd, yielded a fixed dose of 4.0 mg.

### **1.7.3 Rationale for including an MLN9708 + Rd cohort**

Since this study will be the first clinical study of MLN9708 in Japan, we decided to first investigate the tolerability, safety and pharmacokinetics of MLN9708 in monotherapy. However, in the treatment of relapsed or refractory multiple myeloma, proteasome inhibitors, immunomodulators and steroid combination therapies are commonly used. The combined use of bortezomib, lenalidomide and low-dose dexamethasone (VRd) therapy in multiple myeloma has been confirmed to be safe and effective (Anderson et al, 2010; Kumar et al, 2010; Richardson et al, 2010a; Richardson et al, 2010b). MLN9708, a new proteasome inhibitor, is expected to possess pharmacological efficacy and safety superior to that of bortezomib. In study C16005, a study of the combined use of MLN9708 with Rd, not only did 15 of 15 subjects achieve PR or better response, but good safety results were obtained in all subjects as well. Given this result, a global phase 3 study of the combined use of MLN9708 with Rd (study C16010) is currently being planned. Consequently, in this study, in addition to investigating MLN9708 monotherapy, we decided to also investigate MLN9708 when used in combination with Rd. For the dosages of Rd, we used the dosages used in overseas clinical studies in which the efficacy and safety of VRd therapy were confirmed. Comparison of the efficacy and safety of dexamethasone in 445 newly diagnosed multiple melanoma patients overseas between a group of 223 patients who received high-dose dexamethasone (40 mg/day on Days 1-4, 9-12, and 17-20) and a group of 222 patients who received low-dose dexamethasone (40 mg/day on Days 1, 8, 15, and 22) revealed that low-dose dexamethasone afforded a level of efficacy similar to that obtained with high-dose dexamethasone (Rajkumar et al, 2010). Weekly low-dose dexamethasone was therefore selected.

### **1.7.4 Rationale for the initial doses and cohorts**

In study C16004, Grade 3 adverse events were reported in 2 of 6 subjects at the MTD of 2.97 mg/m^2 (equivalent to 5.5 mg), but Grade 3 or higher adverse events were not reported at the next lowest dose of 2.23 mg/m^2 (equivalent to 4.0 mg). Therefore, in this study, we decided to use 4.0 mg at the initial dose (cohort 1). For the MLN9708 + Rd cohort (cohort 2), we selected a dose of 4.0 mg + Rd, which was the recommended dose in the MLN9708 + Rd phase 3 study and the phase 2 part of study C16005, and was the next dose level below the MTD of 2.97 mg/m^2 (equivalent to 5.5 mg) in study C16005.

Furthermore, we have also established a monotherapy cohort that will receive 5.5 mg (cohort 3) and a MLN9708 + Rd cohort that will receive 5.5 mg + Rd (cohort 4) in order to confirm the tolerability in Japanese at the dose equivalent to the MTD overseas once the tolerability of 4.0 mg and 4.0 mg + Rd have been confirmed.

### **1.7.5 Rationale for once-weekly dosing**

Based on the nonclinical and clinical study results, we selected a 28-day MLN9708 dosing cycle with weekly oral dosing on Days 1, 8, and 15 and no dose given on Day 22. In a mouse model, peak antitumor activity was obtained with weekly dosing, and the results of multiple-dose toxicity studies also support the case for weekly dosing. MLN9708 weekly dosing was confirmed to be tolerable in study C16004 in relapsed or refractory multiple myeloma.

Since the global phase 3 study that is currently being planned (study C16010) will also employ a similar dosing method, we have decided to confirm the tolerability of such a dosing method in this study.

## **2. OBJECTIVES**

### **2.1 Primary Objective**

To evaluate the tolerability, safety, and pharmacokinetics of MLN9708 alone or in combination with Rd in patients with relapsed and/or refractory multiple myeloma.

### **2.2 Secondary Objective(s)**

To evaluate the antitumor activity of MLN9708 in patients with relapsed and/or refractory multiple myeloma.

### **3. EXPERIMENTAL PLAN**

#### **3.1 Study Design**

This is a phase 1, multicenter, single-arm, open-label, dose-escalation study to evaluate the tolerability, safety, and pharmacokinetics of MLN9708 administered alone or in combination with Rd in patients with relapsed and/or refractory multiple myeloma. This study consists of the following 4 cohorts.

- Cohort 1: MLN9708 4.0 mg
- Cohort 2: MLN9708 4.0 mg + Rd
- Cohort 3: MLN9708 5.5 mg
- Cohort 4: MLN9708 5.5 mg + Rd

Three subjects will be enrolled sequentially from cohorts 1 (MLN9708 4.0 mg alone) to 4. If a DLT occurs in one subject during DLT-assessment period, 3 additional subjects will be enrolled in the applicable cohort to evaluate the tolerability in a total of 6 subjects. If DLT occurs in 2 of the 3 subjects, the given dosage is considered intolerable. If DLT occurs in 2 of the 6 subjects, the sponsor will determine the tolerability to the given dosage after discussing with the Efficacy and Safety Evaluation Committee (ESEC).

The sponsor will evaluate the tolerability of MLN9708 on the basis of the safety data including DLT incidences during the DLT-assessment period. The sponsor will decide whether the next cohort will be studied and the dose of the next cohort in consultation with the ESEC, if necessary. If the current cohort is considered tolerable, the next cohort will be in the order of cohorts 2 (MLN9708 4.0 mg + Rd), 3 (MLN9708 5.5 mg alone), and 4 (MLN9708 5.5 mg + Rd). Even if a dosage is considered tolerable and transition to the next cohort is considered feasible, the next cohort may not be studied based on the results of the overseas clinical studies and the current study.

The additional written informed consent for extended treatment will be obtained before the first dose of MLN9708 in Cycle 2 from the subjects who meet the criteria in [“6.4 Criteria for Beginning the Next Cycle of Treatment”](#) and have no safety concern.

Subjects who do not give the consent will undergo end of study (EOS) visit on 29 days after the last dose of MLN9708 in Cycle 1. The subjects giving the consent can continue

the study treatment up to 12 cycles unless they meet the criteria in “[8.1 Removal of Subjects](#)” including evidence of progressive disease (PD) and intolerable toxicity. Subjects may remain on treatment after the 12 cycles if the investigator considers it beneficial for the subjects.

All subjects should undergo EOS visit on 29 days after the last dose of MLN9708.

The overall study design is described in “Study Design and Treatment Schema” (page 8).

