#### **3.4.1 Study Duration for Participants**

Study duration for patients will last for up to approximately 14 months, including maximum of 4 weeks screening period, maximum 12 cycles of treatment period (approximately 12 months), and 4 weeks follow-up after the last dose. Subjects may remain on treatment after the 12 cycles if the investigator and the sponsor determine that the subjects would derive benefit from continued therapy beyond 12 months.

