**[General]**

- 24) Patients who do not consent to use adequate contraceptive precautions (e.g. condoms and oral contraceptives) during the following term:
- For women with childbearing potential\*, from when giving their consent through 3 months after the last dose of MLN9708, dexamethasone, or lenalidomide
  - For men having their partners with childbearing potential, from when giving their consent through 4 months after the last dose of MLN9708, dexamethasone, or lenalidomide
- \* Women with child-bearing potential are those who are premenopausal (menopause is defined as the time when there has been no menstrual periods for at least 1 year), or who have not had a bilateral tubal ligation, bilateral oophorectomy, or hysterectomy. The menstruation possibly interrupted by chemotherapy is not defined as menopause.
- 25) Pregnant (e.g. positive for pregnancy test) or lactating. Lactation is prohibited from the first dose through 6 weeks after the last dose of MLN9708, dexamethasone, and lenalidomide
- 26) Use of an investigational medical device within 28 days before enrollment
- 27) Any inabilities that could potentially interfere with the consent or completion of treatment according to this protocol
- 28) Having difficulties in participation to this study by the investigator's judgment

<Basis for setting the criteria>

- (1) To minimize risks and ensure safety of subjects.
- (2) To eliminate any impact on evaluation of MLN9708.
- (3) For unclear potential of reproductive and developmental toxicity associated with MLN9708 and teratogenicity evident by lenalidomide in the Rd cohort.

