## **6.3 Dosage, administration method, dosing schedule**

### **6.3.1 MLN9708 administration**

In this study, MLN9708 will be administered orally once weekly for 3 weeks (on Days 1, 8, and 15 and skip Day 22) in a 28-day cycle for up to 12 cycles.

MLN9708 will be taken on an empty stomach at least 1 hour before or no sooner than 2 hours after a meal.

In Cycle 1, MLN9708 will be given according to the dosage and administration specified in this study protocol; no interruption, delays, or reduction will be permitted.

Missed doses of MLN9708 in Cycle 2 and subsequent cycles can be taken as soon as the patient remembers provided that at least 3 days elapses between doses (until Day 4). If a patient vomits after taking MLN9708, the patient should not repeat the dose, but resume dosing at the time of the next schedule.

Once a dose is reduced, no re-escalation will be permitted.

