### **6.3.3 Dexamethasone Administration (Rd Concomitant Cohort Only)**

Dexamethasone will be administered as a single, oral dose of 40 mg/day weekly on Days 1, 8, 15, and 22 of a 28-day cycle.

Dexamethasone will be taken at approximately the same time each day, approximately 1 hour after MLN9708 and lenalidomide. Each dose of dexamethasone should be taken with food or milk. Dexamethasone should be used according to the package insert of CCI 4 mg.

Missed doses of dexamethasone can be taken as soon as the patient remembers provided that at least 3 days elapses between doses (until Day 4). If the patient vomits after taking a dose, the patient should not repeat the dose but resume dosing at the time of the next schedule.

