## 6.5.2 MLN9708 in combination with Rd

### 6.5.2.1 Criteria for Dose Modification

Dose modifications of MLN9708 are not permitted in Cycle 1. Dose modifications of Rd should be avoided as much as possible. If a subject experiences an adverse event(s) considered strongly related to lenalidomide or dexamethasone and the investigator considers it difficult to continue the treatment with Rd, the investigator and the sponsor will discuss the alternative dose modification.

If dose modification is required in Cycle 2 or subsequent cycles, MLN9708, lenalidomide, or dexamethasone dose will be modified levels according to [Table 6-5](#). If multiple toxicities are noted, the dose should be modified or delayed according to the most severe toxicity guidelines ([Table 6-6](#) through [Table 6-11](#)). Once a dose is reduced, no re-escalation will be permitted.

Each adverse event should be attributed to a specific drug, if possible, so that the dose can be modified accordingly. Reduction of one agent and not the other is appropriate if toxicity is related primarily to one of the agents. Toxicity will be assessed according to the CTCAE version 4.03.

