### **7.2.3 End of study**

The following assessments will be performed on Day 29 after the last dose (acceptable time window + 21 days) for subjects who have received MLN9708. These assessments will be performed before any poststudy therapy is provided. If tests, observations, or examinations are not going to be performed due to some unavoidable circumstance, such as complete withdrawal of subject consent or because follow-up is not possible or the patient has died or is in poor condition, the reason for this will be recorded in the source documents and the study completed. In such cases, the missing tests, observations, or examinations that is to be conducted on Day 29 after the last dose will not be considered protocol deviations.

- ECOG performance status: See [Appendix B](#)
- Vital signs (sitting blood pressure, pulse rate and axillary temperature, SpO2)
- Body weight
- 12-lead ECG (QRS, QT, QTc, PR and heart rate)
  - The 12-lead ECG will be performed with the patient at rest in a supine position.
- Laboratory tests: See [Table 7-1](#) for the test parameters.
  - Hematology tests
  - Chemistry tests
  - Urinalysis
  - Immunoglobulin quantitation (IgG, IgM, IgA, IgD)
  - FLC
- Serum M-protein (protein fraction test by electrophoresis)
- Urine M-protein by 24-hour urine collection (protein fraction test by electrophoresis): Performed only for subjects whose urine M-protein is detected at screening.
- Immunofixation
  - Performed when response confirmation is necessary.
- Pregnancy test (serum or urine; only if the patient is of childbearing potential)
- Adverse events: See “[9.1.1 Adverse Events](#)” to “[9.3 Serious Adverse Event Reporting Procedures](#)”)
- X-rays
  - Bone (head, cervical vertebrae, thoracic vertebrae, lumbar vertebrae, pelvis, both upper arms, both forearms, both femurs, both lower legs); in two directions for each, except for the pelvis
  - X-rays will be performed as appropriate if osteolytic lesions are found at screening.
- CT/MRI (chest, abdomen)
  - If soft tissue plasmacytoma is found at screening, a CT/MRI scan will be performed.
  - All diagnostic imaging scans will be performed using contrast media, except for subjects who are hypersensitive to contrast media or shows concern for potential aggravation of renal dysfunction.

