## **9.2 All Adverse Events Reporting Procedures**

The investigator is responsible for ensuring that all adverse events (as defined in "Section [9.1 Definitions](#)" and as further specified below) observed by the investigator or reported by subjects are collected and recorded in the subjects’ medical records, in the eCRF, and, for serious adverse events, on the serious adverse event report form. These adverse events will include the following:

- All non-serious adverse events (as defined in "Section [9.1.1 Adverse Events](#)") that occur after initiation of investigational product to an end-of-study.
- All serious adverse events (as defined in "Section [9.1.2 Serious Adverse Events](#)") that occur after the subject has signed the informed consent form to an end-of-study, and treatment-related serious adverse events that occur after the end-of-study.

The following adverse event attributes must be assigned by the investigator. The sponsor may ask the investigator to provide follow-up information, extracts from medical record, or eCRFs.

- Adverse event diagnosis or syndrome(s) ( signs or symptoms if not known)
- Event description (with detail appropriate to the event)
- Dates of onset and resolution
- Severity
- Assessment of relatedness to the study treatment
- Action taken
- Outcome

If applicable, the relationship of the adverse event to the study treatment will be assessed by Yes or No.

CTCAE version 4.03 will be used for grading adverse events.

Adverse events requiring follow-up as determined by the investigator will be followed until resolved or considered stable. If the investigator judged that further follow-up is not necessary or follow-up is not possible before the adverse event is resolved or stable, follow-up may be terminated.

It will be left to the investigator's clinical judgment to determine whether an adverse event is related and of sufficient severity to require the subject's removal from treatment or from the study. A subject may also voluntarily withdraw from treatment due to what he or she perceives as an intolerable adverse event. If either of these situations arises, the subject should be strongly encouraged to undergo an end-of-study assessment and be under medical supervision until symptoms cease or the condition becomes stable.

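### In the Rd cohorts the end-of-study visit and most adverse-event collection run from the last MLN9708 dose, so an on-target visit after a full cycle comes 22 days after the last dexamethasone dose

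*Protocol*

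**What the plan says.** Protocol 3.1 sets one rule for all four cohorts: "All subjects should undergo EOS visit on 29 days after the last dose of MLN9708". The Protocol Summary and SAP 5.1 carry the same rule.

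Two other sections do not say which drug starts the clock. Protocol 3.4.1 provides for "4 weeks follow-up after the last dose". Protocol 7.2.3 places the EOS assessments "on Day 29 after the last dose (acceptable time window + 21 days) for subjects who have received MLN9708"; there MLN9708 identifies the subjects to be assessed, not the dose that is counted from.

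The EOS visit also closes most event collection. Protocol 9.2 collects non-serious adverse events "that occur after initiation of investigational product to an end-of-study", and serious events from consent to the same point. Treatment-related serious events are still collected afterwards (9.2, 9.3). The Study Glossary defines a subject's end of study as the last safety follow-up visit, withdrawal of consent or death.

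The three drugs stop on different days of the 28-day cycle. MLN9708 is last given on Day 15 (6.3.1) and lenalidomide on Day 21 (6.3.2). Dexamethasone is given as a "single, oral dose of 40 mg/day weekly on Days 1, 8, 15, and 22 of a 28-day cycle" (6.3.3).

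The drugs can also be modified separately. Section 6.5.2.1 states: "Reduction of one agent and not the other is appropriate if toxicity is related primarily to one of the agents". Tables 6-6 to 6-8 interrupt MLN9708 alone at some steps, and 6.7.3 interrupts it for the rest of the cycle after a DLT.

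**The concern.** The primary objective covers the safety of MLN9708 alone and in combination with Rd. SAP 9.1 tabulates the monotherapy and combination groups. SAP 9.4.2.2 judges relatedness against study treatment, and SAP 9.4.1.2 summarises exposure to all three drugs. SAP 9.4.2.2 puts no end date on treatment-emergent events, so the reporting period is whatever the protocol collects.

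If that period is counted from MLN9708, monotherapy subjects have a target of 29 days after their last study drug. Rd subjects who complete a final cycle have less. New non-serious events, and serious events not judged related, that begin late after lenalidomide or dexamethasone may then fall outside collection. The shortest follow-up could fall on informative subjects: those whose MLN9708 was interrupted after a DLT while Rd went on. Section 6.5.2.1 asks that Rd modification be avoided as far as possible.

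**Working it through.** The 29 days is a set rule, so the plan has no calculation of its own to reproduce. The check is calendar arithmetic on cycle days.

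**Inputs**
- EOS target: 29 days after the last MLN9708 dose (Summary, 3.1, SAP 5.1).
- Visit window: +21 days, later side only (7.2.3).
- Last scheduled doses in a cycle: MLN9708 Day 15, lenalidomide Day 21, dexamethasone Day 22 (6.3.1 to 6.3.3).

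**Formulas**
- EOS cycle day = last MLN9708 day + 29, plus 0 to 21 for the window.
- Follow-up after lenalidomide = EOS cycle day − 21.
- Follow-up after dexamethasone = EOS cycle day − 22.

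**Full final Rd cycle, doses on schedule**
- On target: 15 + 29 = Day 44. After dexamethasone, 44 − 22 = 22 days; after lenalidomide, 44 − 21 = 23 days.
- End of window: 44 + 21 = Day 65. After dexamethasone, 65 − 22 = 43 days; after lenalidomide, 65 − 21 = 44 days.
- If the interval is read as 28 days (the four weeks of 3.4.1), the on-target figures are 21 and 22 days.

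**MLN9708 ends earlier in the cycle**, assuming Rd completes that cycle and MLN9708 is not resumed
- Last MLN9708 on Day 8: 8 + 29 = Day 37, which is 15 days after dexamethasone; with the full window, 58 − 22 = 36.
- Last MLN9708 on Day 1: 1 + 29 = Day 30, which is 8 days after dexamethasone; with the full window, 51 − 22 = 29.

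**All drugs stop together on Day 15:** follow-up is 29 days or more, and there is no shortfall.

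**Clock started at the last dose of any study drug:** 22 + 29 = Day 51.
- After a full cycle this is 51 − 44 = 7 days later than now, and 51 − 15 = 36 days after MLN9708. The current window runs from 29 to 29 + 21 = 50 days after MLN9708, so Day 51 lies inside it.
- In the Day 1 case, Day 51 is 50 days after MLN9708, the last permitted day.

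**The case against.** The strongest reply is that the present anchor is a legitimate choice. MLN9708 is the investigational product. The protocol describes lenalidomide and dexamethasone as approved drugs and lists them as concomitant medications (1.6, 6.2). Every cohort has the same target of 29 days after MLN9708, and the SAP plans descriptive summaries with no formal comparison of regimens. Re-anchoring would make follow-up after MLN9708 itself longer with Rd (36 days after a full cycle) than in monotherapy (29).

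Much of this stands. Outside the unnamed last dose in 3.4.1 and 7.2.3, the plan promises 29 days only after MLN9708; applying that interval to the whole regimen is a benchmark brought to the plan. It does not settle the matter, however. The stated objective is the safety of the combination, relatedness is judged against study treatment, and two sections leave the drug open.

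A reader might infer more than the documents support, in four ways:
- **That Rd follow-up is never more than 22 days.** After a full cycle taken on schedule, 22 days is the least that the rule gives; the one-sided window extends it to 43.
- **That late events are missed selectively in the Rd cohorts.** Related serious events are collected after EOS, and 9.2 follows events needing follow-up until they are resolved or stable. DLT assessment ends at Cycle 2 Day 1 (6.7.1) and is untouched. Nothing in the documents estimates how many events would be lost.
- **That the 8-day case is an expected course.** The sentence in 6.5.2.1 concerns reduction, not stopping. Tables 6-6 to 6-8 envisage resuming MLN9708, and a resumed dose restarts the clock. The plan does not say whether Rd may continue once MLN9708 is permanently stopped.
- **That the contraception criterion contradicts the EOS rule.** Criterion 24 in 4.2 does count "through 3 months after the last dose of MLN9708, dexamethasone, or lenalidomide" for women, but its stated basis is reproductive toxicity and teratogenicity. It sets no standard for adverse-event follow-up.

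**Conclusion.** The concern holds as a modest design and consistency point. In the Rd cohorts the EOS visit is tied to MLN9708 in three places and to an unnamed last dose in two. It ends collection of non-serious events and of serious events not judged related.

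In the usual case the on-target visit falls 29 − 22 = 7 days short of a 29-day interval after dexamethasone, and 29 − 23 = 6 days short after lenalidomide. The window permits a later visit but does not require one, and 7.2.3 asks that the assessments precede any poststudy therapy, which may favour earlier visits. The 15-day and 8-day figures are possible extremes that rest on the two assumptions given with them. The supportable conclusion is that some late events may go uncollected after the combination; how many is unknown.

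**What to change.** Reconcile the Protocol Summary, 3.1, 3.4.1, 7.2.3 and SAP 5.1 on which dose starts the clock. For the Rd cohorts, state that the EOS visit, and with it adverse-event collection under 9.2, runs from the last dose of any study drug (MLN9708, lenalidomide or dexamethasone). Leave monotherapy unchanged. Section 8.1, which counts to the 29th day after the last dose of investigational product, needs matching wording.

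The cost is amendment text and a visit about 7 days later after a full Rd cycle. There are two real downsides. Follow-up after MLN9708 becomes longer in Rd than in monotherapy, so the report should give follow-up from both anchors. Assessments that must precede poststudy therapy also come later.
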